#### 7.2.1.4.2. Safety

For safety endpoints, the as-treated population will be used at the IL.

#### 7.2.1.4.3. PK

For PK endpoints, the PK analysis set will be used at the IL.

#### 7.2.1.4.4. Baseline Variables

For baseline variables, the as-treated population and the modified as-treated population will be used at the IL.

#### 7.2.1.5. Analysis Methods

##### 7.2.1.5.1. Cumulative Incidence of MMR at 12 Months

The cumulative incidence of MMR at 12 months will be estimated using the cumulative incidence method described in [Section 6.3.3](#).

##### 7.2.1.5.2. MMR by 12 Months

The MMR by 12 months will be summarized described in [Section 6.2.1](#).

##### 7.2.1.5.3. MMR at 3, 6 and 9 Months

The MMR at 3, 6 and 9 months will be summarized described in [Section 6.3.1](#).

##### 7.2.1.5.4. MR^1 at 3 Months

The MR^1 at 3 months will be summarized described in [Section 6.3.2](#).

##### 7.2.1.5.5. Safety Endpoints

All safety endpoints will be summarized described in [Section 6.6](#).

##### 7.2.1.5.6. PK Endpoints

All PK endpoints (excluding the Exposure-Response relation) will be summarized described in [Section 6.2.6](#).

##### 7.2.1.5.7. Baseline Variables

Baseline variables will be summarized described in [Section 6.5](#).

#### **7.2.1.6. Prevention of Any Bias**

The results from the IL will not be reported to the study monitors and site staff including investigators to prevent the mixture of any bias.

#### **7.2.2. Primary Analysis**

The PA will be conducted after Core Treatment Phase of all treated patients and before the FA. All analyses described in this SAP including the primary efficacy analysis of the primary endpoint will be performed at the PA unless otherwise specified. No adjustment of the significance level will be needed because no formal analysis is planned at the FA.

#### **7.2.3. Final Analysis**

The FA will be conducted after releasing the study database. The endpoints described below will be reported at the FA.

- MMR by 18 months;
- Duration of MMR and CCyR;
- EFS (both on-treatment and off-treatment);
- OS;
- MMR at 18 months;
- Time to MMR, MR4.0, MR4.5 and CCyR;
- Time to transformation to AP and BP CML on treatment;
- Type of mutations present at treatment completion/discontinuation or suboptimal response;
- All safety endpoints.

No statistical hypothesis test will be planned at the FA.

#### **7.2.4. Periodic Safety Review**

The team will review individual and summary data collected in the safety and clinical databases for periodic safety review.

## 9. APPENDICES

### Appendix 1. Response Definitions

#### Appendix 1.1. Molecular Responses

Before Treatment	Molecular Response	RT-PCR (BCR-ABL Ratio)
Chronic Phase	Major, or MMR	≤0.1% (corresponding to ≥3 log reduction from baseline a ) with a minimum number of ABL transcripts specified by the central laboratory
	MR 	A 1 log reduction in BCR-ABL transcript with a minimum number of ABL transcripts specified by the central laboratory
	MR 	A 2 log reduction in BCR-ABL transcript with a minimum number of ABL transcripts specified by the central laboratory
	MR 4.0	Either (i) detectable disease with ≤0.01% BCR-ABL IS or (ii) undetectable disease in cDNA with a minimum number of ABL transcripts specified by the central laboratory
	MR 4.5	Either (i) detectable disease with ≤0.0032% BCR-ABL IS or (ii) undetectable disease in cDNA with a minimum number of ABL transcripts specified by the central laboratory in the same volume of cDNA used to test for BCR-ABL

a. Standardized baseline from central laboratory.

#### Appendix 1.2. Cytogenetic Responses

Before Treatment	Cytogenetic Responses a	Percent of Ph+ Cells
Chronic Phase	None	>95%
	Minimal	66%–95%
	Minor	36%–65%
	Partial	1%–35%
	Complete	0%
	Major	Complete + Partial Rates

a. Based on analysis of at least 20 metaphases.

#### Appendix 1.3. Blast Phase and Accelerated Phase

Patient meeting any of the following criteria will be judged as either a BP or an AP.

Phase	Criteria
Blast Phase	
 
• <math>\geq 30\%</math> blasts in blood or bone marrow.
 
• Extramedullary blast proliferation, other than in spleen.
 

Accelerated Phase	
 
• 15%–29% blasts in blood or marrow, or <math>>30\%</math> blasts plus promyelocytes in blood or marrow with blasts <math><30\%</math>.
 
• <math>\geq 20\%</math> basophils in blood.
 
• Persistent thrombocytopenia (<math><100 \times 10^9/L</math>) unrelated to therapya.
 
• Clonal chromosome abnormalities in Ph+ cells (CCA/Ph+), major route, on treatmentb.
 

- a. Persistent thrombocytopenia is not considered to define AP progression as the database does not collect data regarding the relationship between the platelet value and therapy.
- b. Clonal chromosome abnormalities alone are not considered sufficient to define progression to AP unless concurrent presence of another AP criterion.

#### Appendix 1.4. Hematologic Responses

Hematologic Responses a	Definition
Complete Hematologic Response, or CHR	
 
• <math>WBC \leq 10 \times 10^9/L</math>.
 
• Basophils <math><5\%</math> in blood.
 
• No myelocytes, promyelocytes, myeloblasts in the blood differential.
 
• Platelet count <math><450 \times 10^9/L</math>.
 
• Spleen non palpableb.
 

- a. Had to meet all criteria indicated in the Definition column
- b. In the absence of extramedullary disease info, it is assumed that that spleen is non-palpable.

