- j. ECHO or MUGA to be performed at screening (within 2 weeks prior to registration) and at End of Treatment/Withdrawal or at Week 96, whichever is earlier. If a patient has undergone ECHO or MUGA as standard of care prior to entering the study, the procedures will not have to be repeated if results are available and the procedures were performed within 28 days prior to registration. To enable meaningful clinical comparison, every effort must be made to ensure that the imaging method used to assess cardiac function remains consistent for each individual patient through the course of the trial.

- k. Hematology including automated complete blood count (CBC) (eg, hemoglobin, RBC, WBC, platelets and hematocrit) with differential counts (eg, neutrophils, lymphocytes, monocytes, eosinophils, basophils, metamyelocytes, myelocytes, promyelocytes, myeloblasts, unspecified blast cells and band cells) to be performed locally. Hematology assessments are to be performed at Screening, Weeks 1, 2, 3, 4, 6, 8, 10, 12, 16, 20, 24 and then every 12 weeks for the next 72 weeks (ie, until the end of Year 2), then every 24 weeks, and End of Treatment/Withdrawal visit. CHR must be confirmed by 2 assessments at least 4 weeks apart. Hematology to be repeated at least 4 weeks after achieving first CHR.
- l. Chemistry panel to be performed locally including: sodium, potassium, chloride, carbon dioxide or bicarbonate (if available), blood urea nitrogen (BUN) or urea, creatinine, glucose, total protein, albumin, calcium, alkaline phosphatase, amylase, lipase, phosphorous or phosphate, and magnesium. Creatine kinase (CK) also to be performed locally. Abnormally high CK values should be confirmed and fractionated (where possible). Uric acid to be obtained until patient achieves a CHR. Supplementation is advised for potassium levels or magnesium levels below the lower limit of normal (LLN), with consideration of the patient's underlying renal function.
- m. Liver Function tests to be performed locally including: total bilirubin, aspartate aminotransferase (AST) and alanine aminotransferase (ALT).
- n. Coagulation panel to be performed locally including: prothrombin time (PT) expressed as either PT or international normalized ratio (INR) and partial/activated partial thromboplastin time (PTT or aPTT).
- o. The first dose of study drug should occur no later than 3 business days after registration of the patient, with the day of first study drug administration = Day 1.

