7.1. Efficacy Assessment

7.1.1. Efficacy Assessment Methods

Efficacy will be determined by physical examination, analysis of peripheral blood and bone marrow. Automated CBC (eg, hemoglobin, red blood cell (RBC), WBC, platelets, and hematocrit), differential counts (eg, neutrophils, basophils, eosinophils, lymphocytes, metamyelocytes, myelocytes, monocytes, promyelocytes, myeloblasts, unspecified blast cells and band cells), bone marrow differential (eg, plasma cells, promyelocytes, myelocytes, metamyelocytes, eosinophils, lymphocytes, monocytes, myeloblasts, erythroblast, basophil, neutrophils, band neutrophils, unspecified blast cells, megakaryocytes, and erythroid precursors), molecular analysis for BCR-ABL transcripts, cytogenetics, physical examination, and mortality will be used to determine the response to treatment as described in [Appendix 2](#). Molecular and hematologic response rates will be assessed for all patients. Cytogenetic response will be assessed in all Ph+ CML patients. The timing of these assessments is presented in the [SCHEDULE OF ACTIVITIES](#) table.

Molecular response monitoring using RT-qPCR for BCR-ABL copy number will be performed on peripheral blood on all patients harboring b2a2 and/or b3a2 transcripts and will be sent to a central vendor for performance and assessment on the IS; sample collection for molecular response monitoring is described in Section [7.1.1.1](#).

Differential count and cytogenetic assessment on bone marrow aspirate will be performed locally.

Bone marrow obtained as part of standard of care prior to signing the informed consent document may be used at screening as long as it was collected within 28 days prior to registration. Patients completing treatment for cytogenetically confirmed treatment failure do not need to repeat bone marrow at treatment completion. Patients ending treatment for reasons other than cytogenetically confirmed treatment failure must undergo treatment completion bone marrow aspirate if the previous bone marrow aspirate was performed >12 weeks prior to treatment failure. Additional bone marrow aspirations and cytogenetics will be done as indicated (eg, suspect disease progression or failed/inadequate Week 48

[Month 12] assessment). If confirmed loss of MMR occurs in combination with a $5 \times$ PCR increase for BCR-ABL, a bone marrow aspirate for cytogenetics should be obtained.

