7.2.3. Laboratory Safety Assessment

Hematology and blood chemistry will be drawn at the time points described in the [SCHEDULE OF ACTIVITIES](#) table and analyzed at local laboratories.

Table 4. Safety Laboratory Tests

Hematology	Chemistry	Coagulation	Urinalysis****	Pregnancy Test
Hemoglobin	ALT	PT or INR	Urine dipstick for urine protein: If positive and clinically indicated, collect 24-hr and microscopic (Reflex Testing)	For female patients of childbearing potential, serum or urine
Platelets	AST	PTT or aPTT		
Hematocrit	Alk Phos			
RBC	Sodium			
WBC	Potassium			
Neutrophils	Magnesium			
Lymphocytes	Calcium			
Monocytes	Chloride			
Eosinophils	TBili*			
Basophils	BUN or Urea			
Metamyelocytes	Creatinine**			
Myelocytes	Creatine kinase			
Promyelocytes	Fractionated creatine kinase if creatine kinase is abnormally high (if available)		Urine dipstick for urine blood: If positive and clinically indicated, collect a microscopic (Reflex Testing)	
Myeloblasts				
Unspecified blast cells				
Band Cells	Uric Acid***			
	Glucose (nonfasted)			
	Albumin			
	Phosphorous or Phosphate			
	Total protein			
	Amylase			
	Lipase			
	Carbon dioxide or bicarbonate (if available)			
	Other Tests: HBV and HCV			

Abbreviations: ALT = alanine aminotransferase; aPTT = activated partial thromboplastin time; AST = aspartate aminotransferase; BUN = blood urea nitrogen; HBV = hepatitis B virus; HCV = hepatitis C virus; INR = international normalized ratio; PT = prothrombin time; PTT = partial thromboplastin time; RBC = red blood cell count; TBili = total bilirubin; WBC = white blood cell count.

* For potential Hy's Law cases, in addition to repeating AST and ALT, laboratory tests should include albumin, creatine kinase, total bilirubin, direct and indirect bilirubin, gamma-glutamyl transferase, PT/INR, alkaline phosphatase, total bile acids and acetaminophen drug and/or protein adduct levels. ** eGFR will be calculated. *** Uric acid will be obtained until patient achieves a CHR. **** Urinalysis and microscopic (Reflex testing) may include urine protein, urine pH, urine blood/hemoglobin, urine glucose, urine esterase, urine nitrites, urine ketones, urine specific gravity, urine red blood cells, urine white blood cells, urine crystals and urine casts.

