### 3.2.4. EFS

The EFS is measured from the date of first dose until the first occurrence of one the following events, censored at the earlier of the last valid hematologic or cytogenetic assessment for those without events:

1. Death due to any cause;
2. Transformation to AP or BP (on treatment; see [Appendix 1.3](#));
3. Loss of CHR.
  - Loss of CHR is defined as the appearance of any of the following, confirmed by a second determination  $\geq 4$  weeks later (unless associated with CML-related treatment discontinuation):
    - WBC count that rises to  $>20.0 \times 10^9/L$ ;
    - Pplatelet count that rises to  $\geq 600 \times 10^9/L$ ;
    - Appearance of palpable spleen or other extramedullary involvement proven by biopsy;
    - Appearance of 5% myelocytes in the peripheral blood, or

- Appearance of blasts or promyelocytes in the peripheral blood.
4. Loss of CCyR (unless associated with CML-related treatment discontinuation; refer to [Section 3.2.3](#) for the definition of loss of CCyR), or
  5. For patients not achieving a CHR: doubling of white blood cell (WBC) at least 1 month apart with the second value  $>20 \times 10^9/L$  and maintained in subsequent assessments for at least 2 weeks.

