#### **5.3.3. Hematologic Response Assessment**

Handling of missing hematology data will take the following steps:

1. For each patient, the observations are sorted by visit and the relative day.
2. For each observation, the peripheral blood differentials should add up to 100%. Some sites may not record 0%. Instead, the corresponding field may appear as missing or “ND.” If myelocytes, promyelocytes and myeloblasts in the blood differential are reported as missing or “ND,” the following rule will be applied. Each domain of the differentials will be summed together. If the total is between 98.5% and 101%, the missing values will be assigned 0%. Otherwise, the observation will be left as is and the record will also be reported as a data issue.
3. If CHR cannot be assessed due to one or more missing components of CHR, impute CHR if a patient has a MMR or a CCyR and all assessed components of CHR are within appropriate limits.

Furthermore, in the absence of extramedullary disease info, it is assumed that spleen is non-palpable.

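### The SAP's CHR definition does not exclude unspecified blast cells, although the differential lists them as a separate item and the loss-of-CHR rule counts any blasts

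*SAP*

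**What the plan says.** - **CHR criterion.** SAP Appendix 1.4 requires "No myelocytes, promyelocytes, myeloblasts in the blood differential", together with limits on WBC, basophils and platelets and a non-palpable spleen. Table A in Protocol Appendix 2 names the same three cell types.
- **What the differential contains.** Footnote k of the Protocol Schedule of Activities lists "metamyelocytes, myelocytes, promyelocytes, myeloblasts, unspecified blast cells and band cells) to be performed locally". Protocol 7.1.1, on efficacy methods, lists "metamyelocytes, myelocytes, monocytes, promyelocytes, myeloblasts, unspecified blast cells and band cells". Both lists are given as examples, but Protocol Table 4 has a separate entry for "Unspecified blast cells" alongside the one for myeloblasts.
- **Loss of CHR.** One of the triggers in SAP 3.2.4 is "Appearance of blasts or promyelocytes in the peripheral blood", with no restriction to myeloblasts. Protocol 6.5 and 9.2.2.4 use the same trigger.
- **Missing differential fields.** Step 2 of SAP 5.3.3 opens with "If myelocytes, promyelocytes and myeloblasts in the blood differential are reported as missing" (or recorded as ND). It then adds up all fields of the differential: "If the total is between 98.5% and 101%, the missing values will be assigned 0" percent.
- **Confirmation.** Protocol 7.1.1 requires CHR to last at least 4 weeks and to be confirmed by two assessments at least 4 weeks apart, using local laboratory results.

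**The concern.** The differential has two places in which blasts can be recorded, and the CHR criterion tests only one of them. A programmer who follows Appendix 1.4 would check three fields and ignore the fourth. A laboratory that counts blasts without assigning a lineage could therefore produce a sample that passes the criterion with blasts in the blood. The rule for losing the response uses the broader word, so the same sample would show a finding that counts toward loss.

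What is at stake is the cumulative CHR rate, where the error can only raise the figure. There is also an indirect route to the secondary endpoint EFS. CHR status decides whether a patient is assessed for loss of CHR or under the WBC-doubling rule, which applies to patients who have not reached CHR.

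**Working it through.** The documents give no figure that depends on this definition, so there is none to reproduce. The check applies SAP 5.3.3 step 2 and the Appendix 1.4 criteria literally to constructed differentials.

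**Assumed sample.** WBC 6 and platelets 250 (both × 10⁹/L), spleen non-palpable. With b the percentage of unspecified blasts:

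- neutrophils 65 − b, lymphocytes 25, monocytes 7, eosinophils 2, basophils 1;
- metamyelocytes, bands, myelocytes and promyelocytes all 0;
- myeloblasts either blank or recorded as 0.

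Total = (65 − b) + 25 + 7 + 2 + 1 + b = 100%, whatever the value of b.

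**Present wording.** b was set to 1, 2, 5, 10 and 14, with each of the two myeloblast entries, which gives 5 × 2 = 10 cases.

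| Myeloblast field | Zero-fill applied? | CHR criteria met | Blast finding under loss of CHR |
|---|---|---|---|
| Blank | Yes, total of 100% lies within 98.5% to 101% | 5 of 5 | 5 of 5 |
| Recorded as 0% | Not needed | 5 of 5 | 5 of 5 |

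The two rows agree, so the definition is the cause. Zero-fill only fails to prevent the result, because unspecified blasts count toward the total that it checks.

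**Unspecified blasts also excluded** (a blank in that field read as none recorded). All 10 cases change to CHR not met, with no change to step 2.

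**When zero-fill does protect.** If cells are recorded in no field at all, shortfalls of 2% and 5% give totals of 98% and 95% and the fill is blocked. Shortfalls of 1% and 1.5% give 99% and 98.5% and it is allowed.

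**Accelerated-phase backstop.** The blast criterion in SAP Appendix 1.3 starts at 15%, so it catches none of the values from 1% to 14%.

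**Size per patient.** With the planned 60 patients in the modified as-treated population, one patient is 1/60 = 1.7 percentage points. With about 3 Ph− patients added, the as-treated figure is 1/63 = 1.6 points. Both are ceilings. The endpoint is cumulative, so a patient credited wrongly at one time who has a genuine confirmed CHR at another is a responder either way, and the rate does not move.

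**The case against.** The strongest case on the other side is that this is a matter of terminology with little practical reach.

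- **One sample never establishes CHR.** This stands. The pattern must recur, or pair with a clean sample, across two assessments at least 4 weeks apart. A laboratory that habitually uses the unspecified field could repeat it, but the documents do not show how often that happens.
- **The profile is narrow.** This also stands. It needs blasts with no myelocytes or promyelocytes recorded, and WBC, platelets, basophils and spleen all within limits.
- **The data structure is partly unseen.** Two of the three lists are examples, no CRF specification is available, and programmers may group the blast fields. Table 4 nevertheless lists the two items separately, and neither plan states any grouping.

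Three stronger readings are tempting, and the documents do not support them:

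- A reader might infer that the zero-fill rule turns blasts into a response. It does not. The result is the same when myeloblasts are recorded as 0%, and where cells are left unrecorded the total check blocks the fill for the larger shortfalls.
- A reader might infer that every affected patient adds 1.7 points. That is a ceiling, because the endpoint is cumulative.
- A reader might infer that EFS will record losses of responses that were never reached. That would need a falsely confirmed CHR, and then a loss that is itself confirmed at least 4 weeks later or linked to CML-related treatment discontinuation. The trigger also speaks of the appearance of blasts, and blasts already there when CHR was credited have not plainly appeared.

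**Conclusion.** The point holds as a gap in the definition. Taken literally, SAP Appendix 1.4 lets a sample with unspecified blasts below 15% satisfy the CHR criteria, while SAP 3.2.4 treats the same finding as a sign of loss.

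The effect on cumulative CHR is upward only and at most 1.7 points per patient. It arises only for a patient who meets the other criteria, has the two supporting assessments, and has no genuine confirmed CHR at another time. The total effect cannot be computed, because the documents do not say how often the unspecified field is used. The conclusion assumes that unspecified blasts are recorded and analysed as a separate field, as Table 4 suggests.

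Cumulative CHR is exploratory and carries no hypothesis test. EFS could be affected only indirectly. The primary endpoint, MMR at 12 months, does not use CHR and is unaffected. This is a minor correction, best made before CHR is derived.

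**What to change.** In SAP Appendix 1.4, for the statistical derivation, read the criterion as no myelocytes, promyelocytes, myeloblasts or unspecified blast cells. CHR and loss of CHR would then use the same blast definition. It can be written as a footnote, which is how that table already handles an unassessed spleen. The derivation should say that the new part fails when a value above 0% is recorded, and that a blank is read as none recorded, as in the check above. No separate change to the zero-fill rule is needed.

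Table A in Protocol Appendix 2 and the loss-of-CHR wording in Protocol 6.5 and 9.2.2.4 must be reconciled with this. CHR also feeds the treatment-failure withdrawal rules in Protocol 6.5, so which blast wording should govern patient management is for the sponsor to settle and is not proposed here.

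The cost is one line in the SAP and one extra field in the derivation. The field is already on the protocol's test list, so no new data collection is planned.

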#### Appendix 1.5. KDIGO Categories

eGFR Category	eGFR (ml/min/1.73 m  )	Terms
1	$\geq 90$	Normal or high
2	60–89	Mildly decreased
3a	45–59	Mildly to moderately decreased
3b	30–44	Moderately to severely decreased
4	15–29	Severely decreased
5	$<15$	Kidney failure

## Appendix 2. Adverse Event of Special Interest

The table below is presented criteria for adverse event of special interest. This was actually used in the study AV001. Though AE criteria listed below were defined using MedDRA version 19.0, the latest version of MedDRA at the time of analysis will be used. Therefore, criteria may possible be updated. Actual criteria used in this study will be reported in the clinical study report.

AE Category	AE Criteria
Cardiac	
 
HLGTs in Cardiac arrhythmias, Heart failures, Pericardial disorders.
 
PTs in Cardiac death, Sudden cardiac death, Sudden death, Ejection fraction decreased.
 
MedDRA SMQ (Narrow): Torsade de pointes/QT prolongation.
 

Oedema	
 
PTs contain Oedema, Weight increased.
 

Effusion	
 
PTs in Pleural effusion, Pericardial effusion.
 

Gastrointestinal	
 
PTs in Nausea, Regurgitation, Retching, Vomiting, Vomiting projectile, Diarrhoea, Defaecation urgency, Frequent bowel movements, Gastrointestinal hypermotility.
 

Diarrhoea	
 
PT in Diarrhoea.
 

Nausea	
 
PT in Nausea.
 

Vomiting	
 
PT in Vomiting.
 

Hemorrhage	
 
PTs in Gastric occult blood positive, Occult blood positive.
 
MedDRA SMQ (Narrow): Haemorrhage terms (excl laboratory terms).
 

Anemia	
 
PTs in Anaemia, Hemoglobin decreased.
 

Neutropenia	
 
PTs in Neutropenia, Neutrophil count decreased.
 

Thrombocytopenia	
 
PTs in Thrombocytopenia, Platelet count decreased.
 

Hypersensitivity	
 
HLGT in Allergic conditions.
 

Hypertension	
 
HLGT in Vascular hypertensive disorders.
 
PTs in Blood pressure abnormal, Blood pressure ambulatory abnormal, Blood pressure ambulatory increased, Blood pressure diastolic abnormal, Blood pressure diastolic increased, Blood pressure increased, Blood pressure systolic abnormal, Blood pressure systolic increased.
 

Infection	
 
SOC in Infections and infestations.
 

Liver Function	
 
MedDRA (SMQ) Hepatic disorders: Sub-SMQs (Narrow) in Cholestasis and jaundice of hepatic origin; Hepatic failure, fibrosis and cirrhosis and other liver damage-related conditions; Hepatitis, non-infectious; Liver related investigations, signs and symptoms (selected relevant).
 
PTs: Alanine aminotransferase abnormal, Alanine aminotransferase increased, Aspartate aminotransferase abnormal, Aspartate aminotransferase increased, Bilirubin conjugated abnormal, Bilirubin conjugated increased, Blood bilirubin abnormal, Blood bilirubin increased, Blood bilirubin unconjugated increased, Hepatic enzyme abnormal, Hepatic enzyme increased, Hepatic function abnormal, Hyperbilirubinaemia, Hypertransaminasaemia, Liver function test abnormal, Transaminases abnormal, Transaminases increased, Blood alkaline phosphatase abnormal, Blood alkaline phosphatase increased, liver function test increased.
 

ALT	
 
PT in Alanine aminotransferase increased.
 

AST	
 
PT in Aspartate aminotransferase increased.
 

Myelosuppression a	
 
MedDRA SMQs (Narrow): Haematopoietic cytopenias affecting more than one type of blood cell, Haematopoietic erythropenia, Haematopoietic leukopenia, Haematopoietic thrombocytopenia.
 
PTs in Bone marrow toxicity, Haematocrit decreased, Haemoglobin decreased, Haematotoxicity, Anaemia.
 

Rash	
 
HLTs in Rashes, eruptions and exanthems NEC; Erythemas; Acnes; Dermatitis and eczema.
 

Renal	
 
HLT in Renal failure and impairment.
 
PTs in Blood creatinine abnormal, Blood creatinine increased, Creatinine renal clearance abnormal, Creatinine renal clearance decreased, Glomerular filtration rate abnormal, Glomerular filtration rate decreased.
 

AE Category	AE Criteria
Vascular	
 
• HLGTS in Coronary artery disorders; Arteriosclerosis, stenosis, vascular insufficiency and necrosis; Embolism and thrombosis.
 
• HLTs in Arterial therapeutic procedures (excl aortic), Central nervous system haemorrhages and cerebrovascular accidents, Central nervous system vascular disorders NEC, Non-site specific vascular disorders NEC, Peripheral vascular disorders NEC (excluding the 2 PTs Flushing and Hot flush), Transient cerebrovascular events, Vascular imaging procedures NEC, Vascular therapeutic procedures NEC.
 

- a. The following MedDRA PTs will be used for cytopenias: anemia (Anaemia), thrombocytopenia (Thrombocytopenia, Acquired amegakaryocytic thrombocytopenia), neutropenia (Cyclic neutropenia, Febrile neutropenia, Idiopathic neutropenia, Neutropenia).

Abbreviations: HLT=high level term; HLG=high level group term; MedDRA=medical dictionary for regulatory activities; NEC=not elsewhere classified; PT=preferred term; SMQ=standard MedDRA query; SOC=system organ class.

